4.3. Lifestyle Requirements

In this study, fertile male patients and female patients who are of childbearing potential will receive PF-06952229. Patients who are, in the opinion of the investigator, sexually active and at risk for pregnancy with their partner(s) must agree to use 2 methods of highly effective contraception throughout the study and for at least 28 days after the last dose of monotherapy (Part 1A and Part 2A) or for at least 3 months after the last dose of combination therapy (Part 1B and Part 2B). The investigator or his or her designee, in consultation with the patient, will confirm that the patient has selected 2 appropriate methods of contraception for the individual patient and his or her partner(s) from the list of permitted contraception methods (see below) and will confirm that the patient has been instructed in their consistent and correct use. At time points indicated in the Schedule of Activities, the investigator or designee will inform the patient of the need to use 2 highly effective methods of contraception consistently and correctly and document the conversation, and the patient's affirmation, in the patient's chart. In addition, the investigator or designee will instruct the patient to call immediately if 1 or both of the selected contraception methods is discontinued or if pregnancy is known or suspected in the patient or partner.

Highly effective methods of contraception are those that, alone or in combination, result in a failure rate of less than 1% per year when used consistently and correctly (ie, perfect use) and include the following:

- 1. Established use of hormonal methods of contraception associated with inhibition of ovulation (eg, oral, inserted, injected, implanted, transdermal), provided the patient or male patient's female partner plans to remain on the same treatment throughout the entire study and has been using that hormonal contraceptive for an adequate period of time to ensure effectiveness.
- 2. Correctly placed copper-containing intrauterine device (IUD).
- 3. Male condom or female condom used WITH a separate spermicide product (ie, foam, gel, film, cream, or suppository). For countries where spermicide is not available or condom plus spermicide is not accepted as highly effective contraception, this option is not appropriate.
- 4. Male sterilization with absence of sperm in the post vasectomy ejaculate.

5. Bilateral tubal ligation/bilateral salpingectomy or bilateral tubal occlusive procedure (provided that occlusion has been confirmed in accordance with the device's label).

All sexually active male patients must agree to prevent potential transfer to and exposure of partner(s) to drug through ejaculate by using a condom consistently and correctly, beginning with the first dose of investigational product and continuing for at least 28 days after the last dose of monotherapy (Part 1A and Part 2A), and for at least 3 months after the last dose of combination therapy (Part 2A and Part 2B).

Patients will be advised to report any reaction to sun exposed skin. In addition, special precautions will be taken to limit any potential photo irritation effect, by minimizing the patients' exposure to light including high intensity ultraviolet B (UVB) light sources such as tanning beds, tanning booths and sunlamps. Patients should be encouraged to apply sunscreen/sunblock daily.

Patients should not eat or drink products containing grapefruit from 7 days prior to enrollment until end of the study or discontinuation.

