3.1.1.5. Part 1B – PF-06952229 in Combination With Enzalutamide in mCRPC

Part 1B is a dose-escalation of PF-06952229 in combination with enzalutamide conducted in patients who were previously treated for mCRPC. The starting dose of PF-06952229 will be based on safety, PK, and potential efficacy, but will not exceed the MTD or MAD of Part 1A. Because of the potential DDI between enzalutamide and PF-06952229, the maximum PF-06952229 dose for the combination may be higher than the monotherapy MTD, but not

higher than 800 mg BID. In addition to safety and tolerability, PF-06952229 PK exposure data may be reviewed for informed dose escalation. Based on evolving PK, PD and safety profiles, assessed in Part 1A, Part 1B may commence before reaching the MTD in Part 1A, and will follow an mTPI design as described in Section 3.1.1.4.

Enzalutamide (a CYP3A4 inducer) is predicted to decrease the PK of PF-06952229 (a CYP3A4 substrate) by 70% (Section 1.2.4). PF-06952229 is not expected to impact the PK of enzalutamide, therefore a fixed dose of enzalutamide is 160 mg QD, administered on a continuous basis. Dose modifications to enzalutamide will not be allowed during the DLT evaluation period.

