3.1.2. Part 2 Dose Expansion

3.1.2.1. Part 2A – Single Agent PF-06952229 in mCRPC

PF-06952229 will be evaluated as a monotherapy in patients with mCRPC in this dose expansion cohort. An additional 10 patients will be enrolled to confirm the safety of the MTD determined in Part 1A (monotherapy dose escalation) and estimate the effect of antitumor activity of PF-06952229 as a monotherapy in patients with mCRPC.

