- 27. For Part 1A Monotherapy Dose Escalation: Pregnant female patients; breastfeeding female patients; fertile male patients and female patients of childbearing potential who are unwilling or unable to use 2 highly effective methods of contraception as outlined in this protocol for the duration of the study and for at least 28 days after the last dose of investigational product.
- 28. For Part 1B Combination Dose Escalation, Part 2A Monotherapy Expansion, and Part 2B Combination Dose Expansion: fertile male patients and female partners of childbearing potential who are unwilling or unable to use 2 highly effective methods of contraception as outlined in this protocol for the duration of the study and for at least 28 days after the last dose for monotherapy (Part 2A) or for at least 3 months after the last dose for combination therapy (Part 1B and Part 2B).
- 29. Inability to consume or absorb study drug, including but not limited to:
 - Active inflammatory gastrointestinal (GI) disease, known diverticular disease or previous gastric resection or lap-band surgery. Impairment of gastro-intestinal function or GI disease that may significantly alter the absorption of PF-06952229, such as history of GI surgery with may result in intestinal blind loops and patients with clinically significant gastroparesis, short bowel syndrome, unresolved nausea, vomiting, active inflammatory bowel disease or diarrhea of CTCAE Grade >1.
- 30. Current use or anticipated need for food or drugs that are known strong and moderate CYP3A4/5 inhibitors, including their administration within 10 days or 5 half-lives of the CYP3A4/5 inhibitor, whichever is longer, prior to first dose of investigational product. A list of CYP3A4/5 inhibitors are provided in Appendix 9 (Section 5.7).
- 31. Current use or anticipated need for drugs that are known strong and moderate CYP3A4/5 inducers, including their administration within 10 days or 5 half-lives of the CYP3A4/5 inducer, whichever is longer, prior to the first dose of investigational product (See Section 5.7). A list of CYP3A4/5 inducers is provided in Appendix 9.

- 32. Have initiated bisphosphonates or approved receptor activator of nuclear factor kappa B -ligand (RANK-L) targeted agents (for example, denosumab) <14 days prior to study entry, unless there is agreement with the medical monitor.

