7.1.1. Pregnancy Testing

All pregnancy tests used in this study, either urine or serum, must have a sensitivity of at least 25 mIU/mL and must be performed by a certified laboratory. For female patients of childbearing potential, 2 negative pregnancy tests are required before receiving PF-06952229 (1 negative pregnancy test at screening and 1 at the baseline visit immediately before PF-06952229 administration). Following a negative pregnancy test result at screening, appropriate contraception must be commenced and the second negative pregnancy test result will then be required at the baseline visit and within 5 days after the first day of the menstrual period (counting the first day of the menstrual period as Day 1) before the patient may receive the PF-06952229. In the absence of regular menstrual bleeding, the study candidate should have used 2 forms of contraception for at least 1 month before the second pregnancy test. Pregnancy tests will also be repeated at every treatment cycle up to Cycle 3 and every other cycle thereafter during the active treatment period, and at the end of study treatment to confirm that the patient has not become pregnant during the study. Pregnancy tests will also be done whenever 1 menstrual cycle is missed during the active treatment period and when potential pregnancy is otherwise suspected, and may be repeated if requested by institutional review boards (IRBs)/ethics committees (ECs) or if required by local regulations. In the case of a positive confirmed pregnancy, the patient will be withdrawn from administration of investigational product but may remain in the study.

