If a study patient is unable to visit the site for protocol-specified safety laboratory evaluations, testing may be conducted at a local laboratory if permitted by local regulations. The local laboratory may be a standalone institution or within a hospital. The safety laboratory evaluations included in Section 7.1.3 may be performed at a local laboratory.

If a local laboratory is used, qualified study site personnel must order, receive, and review results. Site staff must collect the local laboratory reference ranges and certifications/ accreditations for filing at the site. Laboratory test results are to be provided to the site staff as soon as possible. The local laboratory reports should be filed in the patient's source documents/medical records. Relevant data from the local laboratory report should be recorded on the CRF.

If a patient requiring pregnancy testing cannot visit a local laboratory for pregnancy testing, a home urine pregnancy testing kit with a sensitivity of at least 25 IU/mL may be used by the patient to perform the test at home, if compliant with local regulatory requirements. The pregnancy test outcome should be documented in the patient's source documents/medical records and relevant data recorded on the CRF. Confirm that the patient is adhering to the contraception method(s) required in the protocol.

Imaging

If the patient is unable to visit the study site for imaging assessment(s), the patient may visit an alternative facility to have the imaging assessment(s) performed. Qualified study site personnel must order, receive, and review results.

Electrocardiograms

If the patient is unable to visit the study site for ECGs, the patient may visit an alternative facility to have the ECGs performed. Qualified study site personnel must order, receive, and review results.

Study Treatment

If the safety of a trial patient is at risk because they cannot complete required evaluations or adhere to critical mitigation steps, then discontinuing that patient from study treatment must be considered.

PF-06952229 may be shipped by courier to study patient if permitted by local regulations and in accordance with storage and transportation requirements for the PF-06952229. Pfizer does not permit the shipment of PF-06952229 by mail. The tracking record of shipments and the chain of custody of PF-06952229 must be kept in the patient's source documents/medical records.

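### Two reproductive-safety instructions contradict other parts of the protocol: the Part labels in the Section 4.3 condom rule, and the Appendix 8 home pregnancy kit sensitivity

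*Protocol*

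**What the plan says.** **Barrier and contraception rules.** Protocol Section 4.3 contains two distinct rules.

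- The contraception paragraph covers patients who are sexually active and at risk for pregnancy with a partner. They choose two methods from a list of five. For combination therapy the rule runs "for at least 3 months after the last dose of combination therapy (Part 1B and Part 2B". Exclusion 28 in Section 4.2 gives the same Parts: "for at least 3 months after the last dose for combination therapy (Part 1B and Part 2B".
- The condom sentence later in Section 4.3 covers all sexually active men, starts at the first dose, and is meant to keep drug in ejaculate from reaching a partner. For monotherapy it has men "continuing for at least 28 days after the last dose of monotherapy (Part 1A and Part 2A". For combination therapy it applies "for at least 3 months after the last dose of combination therapy (Part 2A and Part 2B".

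The Parts themselves are defined without ambiguity. Section 3.1.2.1, on Part 2A: "PF-06952229 will be evaluated as a monotherapy in patients with mCRPC in this dose expansion cohort". Section 3.1.1.5: "Part 1B is a dose-escalation of PF-06952229 in combination with enzalutamide".

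**Pregnancy tests.** Section 7.1.1 says that all pregnancy tests in the study, urine or serum, "must have a sensitivity of at least 25 mIU/mL" and must be run by a certified laboratory. Appendix 8, on measures during public emergencies, provides that if a patient cannot visit a local laboratory, "a home urine pregnancy testing kit with a sensitivity of at least 25 IU/mL may be used by the patient" at home, subject to local regulation.

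**The concern.** Sites turn both passages directly into instructions to patients. In the condom rule, the Part labels are what a coordinator would look up, and they disagree with the therapy type they are attached to. A man in Part 1B does not find his Part under either period, and a man in Part 2A finds his under both.

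The contraception paragraph and Exclusion 28 do not fill this gap, because they do not themselves require a condom. At stake is whether men in these two Parts are told a clear and consistent duration for avoiding partner exposure after treatment ends. The Part 1B post-treatment visit falls 28 to 35 days after discontinuation, before a 3-month period would end. Compliance after that visit depends largely on what the patient was told.

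For the pregnancy kit, the home test departs from the certified-laboratory requirement of Section 7.1.1, so the kit's sensitivity is the main performance standard left. If a kit met only the Appendix 8 figure, a pregnancy could be missed in a woman who is still being dosed.

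**Working it through.** There is no plan figure to reproduce. The check compares texts and converts one unit.

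**1. Condom rule.** Part labels under each period, by passage:

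| Part | Therapy (Section 3.1) | Condom sentence, 4.3 | Contraception paragraph, 4.3 | Exclusions 27 and 28, 4.2 |
|---|---|---|---|---|
| 1A | Monotherapy | 28 days | 28 days | 28 days |
| 1B | Combination | not listed | 3 months | 3 months |
| 2A | Monotherapy | 28 days and 3 months | 28 days | 28 days |
| 2B | Combination | 3 months | 3 months | 3 months |

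The contraception paragraph and the exclusions agree for every Part. The condom sentence agrees with them for Parts 1A and 2B. It lists Part 2A twice and Part 1B zero times.

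Can the contraception paragraph stand in for the condom sentence? Only one of its five listed methods involves a condom. A couple relying on a copper intrauterine device and a vasectomy would meet the two-method rule without one. The purpose also differs: one rule prevents pregnancy, the other prevents drug transfer. The condom sentence is therefore the text that sets the condom duration.

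**2. Pregnancy kit.** Inputs: 25 mIU/mL (Section 7.1.1) and 25 IU/mL (Appendix 8).

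- Conversion: 25 IU/mL × 1000 mIU per IU = 25,000 mIU/mL.
- Ratio: 25,000 / 25 = 1000.

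Read as a detection limit, the Appendix 8 figure is 1000 times less sensitive than the Section 7.1.1 figure.

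Scope: pregnancy testing is scheduled only in Part 1A, for women of childbearing potential. The home kit comes into play only while Appendix 8 is in force and only when the patient cannot visit a local laboratory. Appendix 8 states that it applies for the duration of the COVID-19 pandemic, so the provision is not merely hypothetical.

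**The case against.** The best case against is that both are clerical slips that a careful reader would resolve. The condom sentence ties its longer period to the last dose of combination therapy. Part 1B is combination therapy, so it is covered by sense; Part 2A patients never take such a dose, so on that reading only the 28-day clause can operate for them. For the kit, Section 7.1.1 speaks of all tests in the study, Appendix 8 refers back to it and nowhere says that it relaxes the sensitivity, and a kit meeting Section 7.1.1 also meets Appendix 8.

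Much of this stands, and it rules out stronger readings that a reader might infer:

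- *That partner exposure in Part 1B is uncontrolled.* It is not. Condom use is required of all sexually active men from the first dose, two-method contraception and Exclusion 28 also apply where relevant, and contraception checks are scheduled during treatment, at end of treatment and at follow-up. Only the post-treatment condom duration is unclear.
- *That about 20 Part 1B and 10 Part 2A patients are affected.* Those are the whole planned cohorts. The rule binds sexually active men only, and their number is not given.
- *That less sensitive kits would in fact be used.* The factor of 1000 describes the two printed units. It does not show what sites would supply.

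What the objection does not do is remove the conflict. Reading by sense means setting aside the printed labels, and a site following the labels would reach a different instruction. Nor does Appendix 8 itself require a kit that meets Section 7.1.1.

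**Conclusion.** Both contradictions are in current operative text and should be corrected. The condom sentence disagrees with the contraception paragraph and Exclusion 28 for two of the four Parts, leaving the post-treatment condom duration ambiguous for sexually active men in Parts 1B and 2A. The home-kit sensitivity in Appendix 8 differs from Section 7.1.1 by a factor of 1000, within the narrow scope described.

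The kit comparison assumes that sensitivity means a detection limit in both places. The number of patients affected cannot be derived from the documents. No endpoint, analysis set, dose decision or statistical result is touched. The documents show that the passages disagree; this review does not decide which period or threshold is right.

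**What to change.** Reconcile the condom sentence in Section 4.3 with the contraception paragraph above it and with Exclusion 28, so that each Part appears under one period only. Reconcile the Appendix 8 kit sensitivity with Section 7.1.1. The sponsor decides the period and the threshold. Then check that the consent form and patient instructions carry the same wording; neither could be examined here. The cost is two text corrections in a protocol amendment plus that check.

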4.4. Sponsor's Qualified Medical Personnel

The contact information for the sponsor's appropriately qualified medical personnel for the study is documented in the study contact list located in the supporting study documentation.

To facilitate access to appropriately qualified medical personnel on study-related medical questions or problems, patients are provided with a contact card. The contact card contains, at a minimum, protocol and investigational product identifiers, patient study numbers, contact information for the investigator site, and contact details for a contact center in the event that the investigator site staff cannot be reached to provide advice on a medical question or problem originating from another healthcare professional not involved in the patient's participation in the study. The contact number can also be used by investigator staff if they are seeking advice on medical questions or problems; however, it should be used only in the event that the established communication pathways between the investigator site and the study team are not available. It is therefore intended to augment, but not replace, the established communication pathways between the investigator site and the study team for advice on medical questions or problems that may arise during the study. The contact number is not intended for use by the patient directly, and if a patient calls that number, he or she will be directed back to the investigator site.

5. STUDY TREATMENTS

For the purposes of this study, and per International Conference on Harmonisation (ICH) guidelines, Investigational Medicinal Product is defined as a pharmaceutical form of an active ingredient or placebo being tested or used as a reference/comparator in a clinical trial, including a product with a marketing authorization when used or assembled (formulated or packaged) in a way different from the approved form, or when used for an unapproved indication, or when used to gain further information about an approved use (ICH E6 1.33).

For this study, the Investigational Medicinal Products are PF-06952229 and enzalutamide.

Refer to the respective IBs for further information on PF-06952229 and enzalutamide.

5.1. Allocation to Treatment

Dose level allocation will be performed by the sponsor after patients have given their written informed consent and have completed the necessary baseline assessments. The site staff will e-mail or fax a complete Registration Form to the designated sponsor study team member or designee. The sponsor will assign a patient identification number and supply this number to the site. The patient identification number will be used on all study-related documentation at the site.

No patient shall receive investigational product until the investigator or designee has received the following information in writing from the sponsor:

- Confirmation of the patient's enrollment;
- Specification of the dose level for that patient and;
- Permission to proceed with dosing the patient.

The sponsor or designee will notify the other sites of the inclusion of a new patient, and will inform study sites about the next possible enrollment date.

5.2. Patient Compliance

On PK clinic days, all doses of study treatments will be administered by the appropriately designated study staff at the investigational site.

Patients will be required to return all unused study treatment at the beginning of each cycle. The number of tablets/capsules returned by the patient will be counted, documented, and recorded.

On drug start and stop days, compliance telephone calls will occur for a minimum of the first 2 cycles to ensure compliance to the study drug schedule. Additionally, a patient diary will be provided to the patients to aid in patient compliance with the dosing instructions and used to support the accountability process. The diary will be maintained by the patient to include missed or changed doses (PF-06952229 and enzalutamide, where applicable). The number of PF-06952229 tablets remaining will be documented and recorded at each clinic visit or Day 1 of each cycle. The patient diary may also be used to support this part of the accountability process.

Enzalutamide will be administered in accordance with the protocol. All PF-06952229 and enzalutamide administration will be documented on the corresponding investigational product administration case report form (CRF). The information regarding diary completion, requirement to return all bottles and accountability documentation will also be performed on patients receiving enzalutamide (where applicable).

5.3. Investigational Product Supplies

PF-06952229 and enzalutamide will be supplied by Pfizer. Study centers will receive PF-06952229 and enzalutamide (for Part 1B and Part 2B) prior to enrollment of the first patient.

The clinical site pharmacy will dispense the supply that is appropriate for the patient.

